AR	Adverse reactions
C&C	Capacity and capability
CAT	Complexity assessment tool
CI	Chief Investigator
CPS	Combined positive score
CR	Complete response
CRF	Case report form
cSCC	Cutaneous squamous cell carcinoma
CTCAE	Common Terminology Criteria for Adverse Events
ctDNA	Circulating tumour DNA
DNA	Deoxyribonucleic acid
ECOG	Eastern Cooperative Oncology Group
EORTC	European Organization for Research and Treatment of Cancer (EORTC)
FFPE	Formalin-fixed paraffin embedded
GCP	Good Clinical Practice
GSTT	Guy's and St Thomas NHS Foundation Trust
HNSCC	Head and neck squamous cell carcinoma
HPV	Human papillomavirus
HTA	Human Tissue Act
KCL	Kings College London
LIPS	Liquid immune profile-based signature
LRBC	Local recurrent breast cancer
MDT	Multidisciplinary team
NA	Not applicable
NASSS	Non-adoption, abandonment, scale-up, spread, and sustainability
NHS	National Health Service
ORR	Objective response rate
OS	Overall survival
PBMC	Peripheral blood mononuclear cells
PD	Progressive disease
PD-L1	Programmed cell death ligand 1
PFS	Progression-free survival
PI	Principal investigator
PR	Partial response
PROM	Patient-reported outcome measure
QLQ	Quality of Life Core Questionnaire
QoL	Quality of life
R&D	Research and Development
RNA	Ribonucleic acid
RT	Radiotherapy
SAE	Serious Adverse Event
SOC	Standard of care
UK	United Kingdom
wIRA	Water-filtered infrared A

4 Summary/Synopsis

Trial Title	Prospective study to assess the real-world implementation of Thermotherapy using wIRA (water-filtered infrared A superficial hyperthermia) in addition to standard of care (SOC) palliative Radiotherapy (RT) in patients with inoperable or incurable cancers	
Short Title	ThermoRad wIRA	
Protocol Version number and Date	Version 2.0, 12 th May 2025	
IRAS Number	327431	
REC Reference	24/SC/0146	
Study Duration	3 years (2 years of recruitment followed by 12 months' follow-up period from the last participant recruited into the study)	
Sponsor name	KCL/GSTT	
Chief Investigator	[name]	
Funder	Dr. med. h.c. Erwin Braun Stiftung Foundation, Switzerland	
Medical condition or disease under investigation	
Inoperable or incurable cancers with at least one lesion suitable for wIRA treatment, consisting of different cohorts of patients:
 
 1) recurrent/metastatic head and neck squamous cell carcinoma (HNSCC) 2) cutaneous squamous cell carcinoma (cSCC) not suitable for radical treatment 3) locally recurrent breast cancer (LRBC) 	
	Objectives	Endpoints

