	4. To assess the median duration of objective response and locoregional control rates of the treated lesion(s) at 6 and 12 months	
4. Duration of Objective Response: Defined as the time from the first documented Complete Response (CR) or Partial Response (PR) to disease progression or metastasis.
 
Locoregional Control Rate: The proportion of patients whose primary tumour site remains free from progression.

	
5. To assess patient-reported outcomes measures (PROMs)
	
5. PROMs assessment using the European Organization for Research and Treatment of Cancer (EORTC) Quality of Life Core Questionnaire (QLQ-C30), European Organisation for Research and Treatment of Cancer Quality of Life Questionnaire Head and Neck Module (QLQ-H&N43) (for HNSCC cohort)
 
PROMs will be collected at baseline, during treatment (after the 3rd fraction of radiotherapy), 6 weeks post-treatment, 12-weeks post-treatment.

	
6. To assess the differences in the efficacy between the lesion(s) treated with radiotherapy with hyperthermia with the lesion(s) treated with radiotherapy alone in those patients with at least 1 additional lesion that is not suitable for treatment with hyperthermia at 6 and 12 months
	
6. Percentage of best ORR, duration of response and disease control rates at 6 and 12 months in the lesion(s) treated with hyperthermia and radiotherapy versus lesion(s) treated with radiotherapy alone.

	
7. To compare clinical outcome of patients treated with superficial hyperthermia in addition to SOC radiotherapy with historical control
	
7. Retrospectively collect data for historical cohort of similar cancer patients treated with SOC radiotherapy alone

Number of Subjects/Patients	
 Up to 60 patients treated with superficial hyperthermia using water-filtered infrared hyperthermia (wIRA) hydrosun® TWH1500 treatment 	

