The patients will receive hyperthermia either once a week or twice a week (as listed in Table 1) using hydrosun® TWH1500 with palliative radiotherapy. The patients will receive hyperthermia treatment for 1 hour before going for palliative radiotherapy as per standard of care. For patients who will undergo 27Gy/6#, they will receive hyperthermia once a week for three weeks during the course of palliative radiotherapy. For patients undergoing 20Gy/5# over five weeks or 36Gy/6# over six weeks, they will receive hyperthermia once a week. For patients undergoing 20Gy/5# over one week or 20Gy/10# over two weeks, they will receive hyperthermia two times per week during their treatment.

Most of the HNSCC patients will be suitable for palliative pembrolizumab (if the tumours are CPS \geq 1) and the cSCC patients will be suitable for cemiplimab if they have an ECOG performance status \leq 1. We would aim to start palliative pembrolizumab within 6 weeks (+/- 2 weeks) of completing palliative radiotherapy if patients are deemed to be suitable and fit for this treatment as part of the standard of care. LRBC patients will undergo systemic treatments as per standard of care according to their previous treatment histories and breast cancer subtypes.

Patients will be assessed during their treatment for toxicities, and rate of adverse events will be assessed by CTCAE version 5.0. Follow-ups and assessment of response will be done as per standard of care.

When appropriate, we will aim to collect biological samples from each patient for translational research (see below) including archival tumour sample, fresh tumour biopsy or resection sample when available, blood samples at different time intervals before, during and after their treatments as well as saliva and mouth swab at the same time points when appropriate. The samples will be analysed to further assess the tumour microenvironment, the peripheral immune response and to identify predictors of treatment response.

For all patients, blood samples will be collected at baseline (at time of consent), before the first round of hyperthermia/radiotherapy treatment*, after the first round of hyperthermia/radiotherapy

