5.1 Schedule of events

	Screening (Visit 0)	Baseline (Visit 1)	Pre-HT (Visit 2)	Post-HT/RT (Visit 3)	6 weeks post HT/RT (Visit 4)	12 weeks post HT/RT (Visit 5)	Disease progression (Visit 6)	10 baseline (Visit 7)	10 – 3wks (Visit 8)	10-6wks (Visit 9)	10-disease progression (Visit 10)	12 months post HT/RT
Eligibility criteria	X											
Participant information	X											
Informed consent		X										
Medical record monitoring		X	X	X	X	X	X	X	X	X	X	X
EORTC QLQ-C30		X		X	X	X						
EORTC QLQ H&N35		X		X	X	X						
Sample collection: blood		X	X*	X	X	X	X	X	X	X	X	
Sample collection: saliva		X	X*	X	X	X	X	X	X	X	X	

*This may be omitted if baseline measures were collected. Omission may occur due to logistical issues (i.e., difficult to arrange with the participant)

Abbreviations: HT, hyperthermia; IO, Immunotherapy; RT, radiotherapy.

- **Treatment visits**

This is an interventional study to implement superficial hyperthermia in the real-world setting, and the patients will continue their clinical visits and follow-up as per normal standard of care. We will obtain the treatment outcome from medical records of patients. It will be during patients' SOC visits that we will collect biological samples and assess PROMs. All patients will be assessed using the European Organization for Research and Treatment of Cancer (EORTC) Quality of Life Core Questionnaire (QLQ-C30). Additionally, the HNSCC cohort will also be assessed using the European Organisation for Research and Treatment of Cancer Quality of Life Questionnaire Head and Neck Module. PROM assessments will take place during the same timepoints as biological sample collection, with the last PROM assessment taking place at 12 weeks post radiotherapy.

8. Subject selection

We will have the following cohorts of patients undergoing standard of care treatments, which we plan to include 15 to 20 patients in each disease cohort* and up to 60 patients in total:

1. HNSCC cohorts

- i. Inoperable/recurrent HNSCC with no previous radiotherapy treatment
- ii. Inoperable/recurrent HNSCC with previous radiotherapy treatment (re-irradiation)

2. cSCC cohort

- i. Inoperable/recurrent cSCC with no previous radiotherapy treatment
- ii. Inoperable/recurrent cSCC with previous radiotherapy treatment (re-irradiation)

3. LRBC cohorts

- i. Inoperable locally recurrent breast cancer with previous radiotherapy treatment (re-irradiation)

* The number of participants may vary between each group

- **Subject inclusion criteria**

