The patient recruitment for the prospective study will initially be 24 months from the commencement of the study at coordinating site, Guy's and St. Thomas' NHS Foundation trust. Thereafter, the patients will be followed up for their long-term treatment outcome and survival as per normal standard of care. We will continue to obtain relevant information on patients' treatment and survival outcome from patients' medical records. The end of the study definition is 12 months from the last participant recruited into the study. We will assess whether the endpoints and outcomes are met at the end of the study, particularly the real-world implementation of superficial hyperthermia (using CE marked water-filtered infrared A (wIRA) machine) in addition to palliative radiotherapy and whether we are able to recruit the target number of patients.

We will submit the protocol for a major amendment towards the end of the study if the study is to continue for up to an additional 3 years of recruitment, providing further funding is obtained. Otherwise, we will analyse all data and produce the final study report at the end of third year.

The criteria for progression beyond the two-year recruitment period are set as below:

1. The study recruits well and reaches the target number of patients (up to 60 patients)
2. The study showed that superficial hyperthermia with wIRA could be implemented in the real-world setting and used in combination with palliative radiotherapy in cancer patients
3. Further funding is obtained to continue beyond the two-year recruitment period

10. Laboratories

Collected patients' samples from Guy's Hospital as part of translational research will be transferred to [name] laboratory at Kings College London for further processing. The samples will be pseudo-anonymised with sample IDs which can be linked to patients. The sample processing will be done by the research assistant appointed for the study and/or [name] lab members and only those with KHP passport will have access to patients' confidential information. The samples will not be transferred or given to anyone without an MTA agreement. However, if there are any successfully generated organoids from any fresh samples, the anonymised organoids may be shared with collaborators. Based on the consent from patients, any other unused blood, saliva, oral swab, urine, and stool samples will be stored at Guy's and St Thomas' head and neck biobank beyond the ethics approval date of the project.

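### The end of study is counted from the last recruitment but the final scheduled time point from the end of treatment, so the last recruits' 12-month review falls after the study has closed

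*Protocol*

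**What the plan says.** **End of study.** The synopsis (Section 4) gives the duration as "3 years (2 years of recruitment followed by 12 months' follow-up period from the last participant recruited into the study". Section 9, End of Study Definition, repeats the rule: "The end of the study definition is 12 months from the last participant recruited into the study". The same section says of the report, if recruitment is not extended: "Otherwise, we will analyse all data and produce the final study report at the end of third year".

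**Last scheduled time point.** The final column of the schedule of events (headed 5.1, within Section 7) is "12 months post HT/RT". It carries one mark, for medical record monitoring. No other column is set at 12 months.

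**Order of consent and treatment.** Section 7 places baseline at consent and ahead of treatment: "blood samples will be collected at baseline (at time of consent), before the first round of hyperthermia/radiotherapy treatment". The longest courses are described as follows: "For patients undergoing 20Gy/5# over five weeks or 36Gy/6# over six weeks, they will receive hyperthermia once a week". The shorter ones are introduced with "For patients undergoing 20Gy/5# over one week or 20Gy/10# over two weeks".

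**Endpoints at 12 months.** Secondary objective 4 (Section 4 and Table 1) concerns "locoregional control rates of the treated lesion(s) at 6 and 12 months". Endpoint 6 compares heated and unheated lesions at the same two times. Neither says from what date the 6 and 12 months run.

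**The concern.** Two clocks are in use. The study's closing date runs from the last recruitment, while the last scheduled review runs from the end of treatment, which is always later. The last participant's 12-month review therefore cannot fall within the study. The same is true of anyone recruited during the final weeks of accrual, for as many weeks as pass between consent and the end of treatment.

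The 12-month results of endpoints 4 and 6 are at stake. The locoregional control rate is defined as a plain proportion, and the protocol states a censoring rule only under progression-free and overall survival. A late recruit who is alive and locally controlled some 10 or 11 months after treatment has no 12-month status to enter. The team would have to omit a scheduled review or collect it after the declared end. The end date also starts the 90-day notice to the ethics committee (Section 15). It is a protocol definition, so a statistical analysis plan could not move it.

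**Working it through.** **Inputs from the protocol**
- Recruitment 24 months, then 12 months from the last recruitment (Sections 4 and 9).
- Target up to 60 patients, 15 to 20 in each of three cohorts, so 45 to 60 (Sections 4 and 8).
- Course length 1, 2, 3, 5 or 6 weeks depending on the schedule (Section 7 and Table 2).

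**Assumptions**
- Recruitment is taken as the date of consent.
- The gap from consent to the first treatment is not given; 0 to 4 weeks is used.
- Accrual is even.
- One month is 52.1775 / 12 = 4.348 weeks.

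**Step 1. The plan's own duration.** 24 + 12 = 36 months, which reproduces the stated three years.

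**Step 2. Shortfall for the last recruit.** Shortfall in months = (gap + course, in weeks) / 4.348. Time since treatment at study end = 12 − shortfall.

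**Step 3. Patients recruited too late.** Number = (60 / 24) × shortfall = 2.5 per month × shortfall. Results are rounded after calculation.

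| Gap (weeks, assumed) | Course (weeks) | Shortfall (months) | Months since treatment at study end | Patients, of 60 |
|---|---|---|---|---|
| 0 | 1 | 0.23 | 11.77 | 0.6 (1.0%) |
| 0 | 3 | 0.69 | 11.31 | 1.7 (2.9%) |
| 0 | 6 | 1.38 | 10.62 | 3.4 (5.7%) |
| 2 | 6 | 1.84 | 10.16 | 4.6 (7.7%) |
| 4 | 1 | 1.15 | 10.85 | 2.9 (4.8%) |
| 4 | 5 | 2.07 | 9.93 | 5.2 (8.6%) |
| 4 | 6 | 2.30 | 9.70 | 5.7 (9.6%) |

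The five-week row with a four-week gap also covers six weekly fractions counted from first to last. With 45 patients (1.875 per month) the range is 0.4 to 4.3 patients.

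**Step 4. Length needed.** For the last recruit to reach 12 months after treatment, the study must run 12.2 to 13.4 months past the last recruitment with no gap, which is 36.2 to 37.4 months in all. With a four-week gap and a six-week course it must run 14.3 months past it, or 38.3 in all.

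**Step 5. What the origin of endpoints 4 and 6 changes.**
- Counted from consent, the last recruit just reaches 12 months at study end, and only the schedule column is missed.
- Counted from the start of treatment, the shortfall is the consent-to-treatment gap.
- Counted from the end of treatment, the table applies.

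The protocol does not choose. Progression-free survival runs from baseline, overall survival from the start of treatment, and the schedule's 12-month column from HT/RT.

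**The case against.** The strongest reply is that endpoints 4 and 6 do not say they need the post-treatment review. Baseline is at consent and progression-free survival runs from baseline, so a 12-month count from consent is an open reading under which nobody is lost to these endpoints. This stands in part. The protocol does not support saying that 12-month status cannot be observed for the last recruits on any reading. But no section adopts the consent origin, and the schedule column would still fall after closure.

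Second, the 12-month time point is a record check and follow-up is routine care, so status at 12 months already depends on when clinic visits fall. That stands and limits the importance of a few weeks. It does not reconcile the two dates.

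Third, Section 9 says that outcome information will go on being obtained from records. That describes the period after recruitment closes. The definition that follows ends the study at 12 months, and nothing extends collection for late recruits.

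Two stronger readings are tempting:
- A reader might infer that every late recruit becomes a missing value. Those who progress locally or die before the cut have a known status, so the counts above are upper bounds.
- A reader might infer that one cohort could lose a quarter to a third of its patients (5/20 or 5/15). This needs the longest course, a four-week gap the protocol does not give, and all five patients in one cohort. With three equally accruing cohorts the last condition has probability (1/3)^4, about 1.2%; the expected number is 5.2 / 3, about 1.7 per cohort. The 5/15 figure also pairs accrual for 60 patients with the cohort size for 45.

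**Conclusion.** The point holds as a mismatch between two protocol definitions. Under every schedule in Table 2, the last recruits' 12-month post-treatment review falls after the end of study, even if treatment starts on the day of consent. This does not depend on the accrual rate, because the end date moves with the last recruit.

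The consequence for endpoints 4 and 6 is conditional: it arises unless their 12 months count from consent. It then affects at most about 1 to 3 of 60 patients with no gap, and about 5 to 6 with an assumed four-week gap and the longest course. Within those numbers, only patients alive and free of local progression at the cut are affected. The counts rest on even accrual and on recruitment meaning consent.

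The primary endpoint, the 6-month time point and the survival summaries, which have a censoring rule, are not harmed. The effect is modest, but it loses information that a change of wording would keep.

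**What to change.** 1. In the synopsis (study duration and end-of-study entry) and in Section 9, define the end of study as the date of the last participant's 12-month record review after hyperthermia and radiotherapy.
2. In Section 4 and Table 1, state that the 6- and 12-month time points of endpoints 4 and 6 count from that same origin.
3. Move the final data cut and the report date to match.

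The cost is a wording amendment and a data cut up to about two months later: 2.3 months in the longest case above (four-week gap, six-week course), 1.4 months with no gap. No visits are added, because the time point uses medical records. Section 15 already allows up to a year after the end of the trial for the final report to the ethics committee.

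Closing recruitment early would not help under the present definition. The end date is tied to the last recruitment and would move forward by the same number of weeks, leaving the shortfall unchanged.
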